8.2 Secondary Outcomes

Objectives	Outcome Measure
The proportion of cases with an actionable mutation based on CSF cfDNA findings using the TARGET (Tumour Alterations Relevant for Genomics-Driven Therapy) database • The concordance between	These will be determined by identifying and quantifying (as a percentage or proportion) actionable mutations found in CSF cfDNA that match a specific gene database, namely TARGET (Tumour Alterations Relevant to Genomics Driven Therapy) gene database. This will be measured by quantifying the genomic
CSF cfDNA and brain metastases for detected mutations The concordance between plasma cfDNA and DNA from breast, extracranial and/or brain metastases for detected mutations (applicable for where brain metastasis has been resected) The concordance between plasma cfDNA and CSF cfDNA for detected mutations.	aberrations in both the CSF cfDNA and plasma cfDNA or tissue sample (primary, extracranial and/or CNS metastasis). The level of agreement will be measures as the number of aberrations observed in both samples as a proportion of all aberrations observed.
To determine the complications post lumbar puncture or aspiration of CSF from an Ommaya reservoir (This will not apply to patients undergoing a lumbar	1 x Patient questionnaire to record complications post- procedure.

IRAS ID: 286155 Page **30** of **73**

puncture at the time of a neurosurgical	Outcomes will be Percentage incidence, percentage
procedure).	severity experiences (i.e. headache, backache, pain
	down leg) and mean duration of experiences will be
	determined.
	1 x Clinician questionnaire to record complications
	post-procedure.
	eCRF will be used to record the date, the ease of the
	procedure complications and the need for intravenous
	fluid and/or analgesia
	Outcomes will be percentage / proportion of patients
	over total recruited patients.
	·

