The advent of genomic medicine has enabled the characterisation of tumours both for the purposes of diagnostics and therapeutics. Notably, the advances in genomic medicine have helped dissect and understand the evolutionary process of cancer by comparing primary cancers with secondary cancers⁹. However, obtaining samples for genomic work in patients with CNS involvement secondary to breast cancer is difficult given the risks and complexity of neurosurgery. The procedure may not be always appropriate given the occurrence of multiple lesions while the increasing use of Stereotactic Radiosurgery (SRS) has reduced the need for surgical resection and so the availability of tissue. In addition, longitudinal tissue sampling during the course of the disease is not possible. The importance of treating the metastases in the brain separately from any prior extracranial metastases has been demonstrated in a recent study of 86 paired primary and brain metastases of which 21 were primary breast cancer and their matched brain metastases¹⁰. This study

IRAS ID: 286155 Page **21** of **73**

demonstrated that while the primary and brain metastases shared a common ancestor, both the primary tumour and the metastasis continued to evolve separately, reflected by the presence of distinct mutations so called "private mutations" ¹⁰. Where the regional lymph nodes, or extracranial metastases were shown not to be reliable surrogates for the oncogenic alterations found in the brain metastases ¹⁰. Inter- and intralesional sampling of the brain metastases demonstrated genetic homogeneity; with brain metastases samples sharing mutations that were not detected in the clinically sampled primary tumour, indicating that the subclones sampled in these lesions were more related to one another than to those detected in the primary tumour. In approximately half of cases, clinically informative alterations which were found in the brain metastases were not detected in the matched primary tumour ¹⁰. These data therefore highlight the need to analyse the brain metastases as a distinct entity rather than relying solely on information from either the primary or the extra cranial systemic disease, as well as opportunities for innovating treatment with targeted agents based on information derived from the brain metastases.

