5.4.2 Secondary objectives

To determine

- The proportion of cases with an actionable mutation based on CSF cfDNA findings using the TARGET (Tumour Alterations Relevant for Genomics-Driven Therapy) database.
- The concordance between CSF cfDNA and brain metastases for detected mutations (applicable where brain metastasis has been resected).
- The concordance between plasma cfDNA and brain metastases for detected mutations (applicable where brain metastasis has been resected).
- The concordance between plasma cfDNA and CSF cfDNA for detected mutations.
- The complications post-lumbar puncture or aspiration of CSF from an Ommaya reservoir (This will not apply to patients undergoing lumbar puncture at the time of neurosurgical procedure).

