13.5 Methods of Analysis

All analyses will be exploratory in nature with descriptive statistics and graphical representations used to communicate all data collected. Continuous data will be expressed as median (IQR) (Range) and categorical data will be expressed as frequencies of counts with associated percentages. Estimated rates statistics will be represented alongside 95% confidence intervals.

IRAS ID: 286155 Page **59** of **73**

14 Data Management and Study Monitoring

For the PRIMROSE CSF Study, the responsibilities for Data Management and monitoring are delegated to LCTC. Separate Data Management and Trial Monitoring Plans have been developed which provide detail regarding the internal processes that will be conducted at the LCTC throughout the trial. Justification for the level of monitoring is provided within those documents and the trial-specific risk assessment. All data will be managed as per local LCTC processes and in line with all relevant regulatory, ethical and legal obligations.

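### Section 8.2 admits primary and extracranial tissue for objectives defined on resected brain metastasis, and its overlap measure does not give the share of brain-metastasis mutations recovered in CSF

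*Protocol*

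**What the plan says.** The secondary objectives (section 5.4.2, repeated in the protocol overview) name one tissue comparator. For CSF: "The concordance between CSF cfDNA and brain metastases for detected mutations (applicable where brain metastasis has been resected"). For plasma: "The concordance between plasma cfDNA and brain metastases for detected mutations (applicable where brain metastasis has been resected").

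The outcome table in section 8.2 differs in two places. Its objective column keeps brain metastases for CSF but rewrites the plasma objective as "The concordance between plasma cfDNA and DNA from breast, extracranial and/or brain metastases for detected mutations", while still limiting it to patients whose brain metastasis was resected. Its outcome column has a single cell for all the concordance objectives, which quantifies "aberrations in both the CSF cfDNA and plasma cfDNA or tissue sample (primary, extracranial and/or CNS metastasis").

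The same cell fixes the statistic: "The level of agreement will be measures as the number of aberrations observed in both samples as a proportion of all aberrations observed". Section 13.5 describes all analyses as exploratory and adds: "Estimated rates statistics will be represented alongside 95% confidence intervals". It names neither an interval method nor a unit of analysis.

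The background in section 5.1 reports that "extracranial metastases were shown not to be reliable surrogates for the oncogenic alterations found in the brain metastases", and that in roughly half of cases clinically informative alterations in the brain lesion were absent from the matched primary. Section 5.2 gives the purpose: to explore CSF cfDNA as a surrogate for the aberrations in brain metastasis.

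**The concern.** The current text gives two definitions of the same objectives. An analyst working from section 5.4.2 would use brain tissue only. One working from the outcome cell in section 8.2 could use any available block. The second course could easily dominate in practice: section 11.1 collects the breast cancer block, and brain or non-cranial biopsies only where available, while section 5.1 notes that radiosurgery has reduced the supply of resected brain tissue.

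The choice matters because the protocol's own background says that primary, extracranial and brain disease diverge. If CSF faithfully reflects the brain lesion, it should disagree with a primary that has evolved separately. A mixed comparator would count that disagreement against CSF.

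The statistic is a second difficulty. A surrogate question asks how much of what is in the brain metastasis CSF shows. An overlap puts brain mutations missed by CSF and extra mutations seen only in CSF into the same denominator, so it cannot tell the two apart.

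**Working it through.** **The plan's own precision figure.** Section 13.2 gives a standard error of 6% for a binary endpoint with 70 patients: √(0.5 × 0.5 / 70) = 5.98%, which agrees. This is a per-patient figure over the whole cohort. It does not carry over to concordance, which is restricted to patients with tissue and counts aberrations. The protocol gives no precision figure for concordance, no expected number of resected patients and no number of aberrations per patient, so everything below uses stated assumptions.

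**Comparator by place in the protocol.**

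| Place | CSF compared with | Plasma compared with |
|---|---|---|
| Overview and 5.4.2 | resected brain metastasis | resected brain metastasis |
| 8.2, objective column | brain metastases | breast, extracranial and/or brain, where brain metastasis was resected |
| 8.2, outcome cell (shared) | plasma, or primary, extracranial and/or CNS tissue | not set out separately |

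**Effect of mixing tissues.** Let f be the fraction of comparators that are brain tissue. Then mean overlap = f × (overlap with brain) + (1 − f) × (overlap with primary).

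| Assumed overlap, brain / primary | f = 1 | f = 0.5 | f = 0.25 | f = 0.1 |
|---|---|---|---|---|
| 80% / 40% | 80% | 60% | 50% | 44% |
| 70% / 50% | 70% | 60% | 55% | 52% |

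CSF's agreement with brain tissue is the same along each row. Only the tissue mix changes.

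**Overlap against recovery.** Overlap = shared / (brain + CSF − shared). Recovery = shared / brain.

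- Brain 8, CSF 10, shared 6: overlap 6/(8 + 10 − 6) = 6/12 = 50%; recovery 6/8 = 75%.
- Brain 10, CSF 8, shared 6: overlap is again 6/12 = 50%, but recovery is 6/10 = 60%. One overlap value fits different recoveries.
- Brain 10, of which CSF finds 8 (recovery 80%): with 0, 5 or 10 CSF-only aberrations the overlap is 8/10 = 80%, 8/15 = 53% or 8/20 = 40%. One recovery fits different overlaps.

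**Intervals, only if aberrations were pooled over patients.** With m aberrations per patient and within-patient correlation ρ, an interval that ignores clustering must be widened by √(1 + (m − 1)ρ). Assume 20 patients, m = 5 and a proportion of 0.5. The 95% half-width ignoring clustering is 1.96 × √(0.25/100) = 9.8 points. Allowing for clustering it is 11.6, 14.5 or 17.0 points at ρ = 0.1, 0.3 or 0.5. If overlap is computed per patient and then summarised over patients, this issue does not arise.

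**The case against.** The best defence of section 8.2 is that its objective column still names brain metastases for CSF. The tissue list sits in a cell serving several objectives and can be read as the set of sample types used across them, with each objective supplying its own comparator. That stands in part. A brain-only CSF comparison is allowed and named, so a reader should not infer that CSF will be compared with any tissue, or that the plan leaves the surrogate question untested. The outcome cell does not secure that comparison, however, and the widened plasma objective contradicts section 5.4.2 on any reading.

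It can also be said that the stated objective is concordance, that shared over all is a legitimate concordance measure, and that surrogacy is only to be explored. That is fair, and the overlap should stay. But section 5.2 states the surrogate aim, the overlap alone cannot answer it, and the counts needed are already collected.

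A reader might go further and infer that the plan pools aberrations over patients, treats them as independent, and will therefore report binomial intervals that are too narrow. The protocol does not support this. Its reference to both samples suits a per-patient calculation, and section 8.3 uses the same formula for paired CSF samples. Section 13.5 specifies no method or unit, and the interval method may properly sit in a statistical analysis plan that is not shown. The widening above is a condition on one possible choice, not a fault in what is written.

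**Conclusion.** Two points hold from the text alone: section 8.2 is inconsistent with section 5.4.2 on the tissue comparator, and the agreement statistic it fixes does not measure recovery of brain-metastasis mutations. Both are written into the protocol rather than left for later.

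The size cannot be derived from the documents. Under the assumptions shown, mixing tissues moves an 80% overlap to between 44% and 60%, or a 70% overlap to between 52% and 60%. The overlap can fall to half of the true recovery (40% against 80%) when CSF carries many aberrations of its own. These are illustrations of direction and possible scale. The outcome is secondary and descriptive, so no test or decision rule depends on it, but the reported concordance would change.

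**What to change.** 1. Reconcile the comparator in section 8.2 with section 5.4.2, for plasma as well as CSF. Use brain-metastasis tissue only for the brain-metastasis objectives, and tabulate concordance with primary and with extracranial tissue separately.
2. Keep the overlap. Beside it, report for each patient the proportion of brain-metastasis mutations detected in CSF and the proportion detected in plasma, and summarise these over patients.
3. State the unit of agreement. If aberrations are pooled over patients instead, the 95% confidence interval must allow for clustering by patient, by a method suited to few patients. A percentile bootstrap over patients is not automatically safe. In simulation (assumed 80% concordance, 10 aberrations each, within-patient correlation 0.1 to 0.5), a nominal 95% interval for the mean patient proportion covered about 79–86% with 6 patients, 87–91% with 10 and 92–93% with 20.

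The cost is a change to the outcome table and a modest amount of analysis on counts already planned; no further samples are needed. The downside is that the brain-tissue comparison will rest on fewer pairs and have wider intervals.

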9.5 Assessments and Follow-up

Once the patient has been registered on the PRIMROSE CSF study, the patient will be scheduled in for a lumbar puncture (with atraumatic needles) or aspiration of CSF from Ommaya Reservoir procedure as soon as is reasonably possible or at the time of neurosurgery if this planned or has been scheduled as part of routine care.

IRAS ID: 286155 Page **35** of **73**

The schedule of assessments is outlined below. The following research data and samples will be collected from the patient:

IRAS ID: 286155 Page **36** of **73**

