10.3 First Lumbar Puncture / Ommaya Reservoir Aspiration Visit

The following procedures will occur at this visit:

- Blood sample collection (1 x 10ml EDTA blood tube and 1 x 10ml SERUM tube) this should be collected immediately before the CSF extraction procedure
- CSF extraction (1 x 10ml CSF tube and 1 x 3ml 5ml CSF tube) this should be carried
 out via Lumbar Puncture or Ommaya Reservoir aspiration as per standard procedure
 (atraumatic needles should be used unless discussed with PI & CI)
- Clinical complications questionnaire (completed by clinical staff via eCRF)

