12.5.1 Reference Safety Information used to Assess Expectedness

This study involves collecting CSF via lumbar puncture (with atraumatic needles) or from aspiration of CSF from in situ Ommaya reservoirs form patients with CNS involvement secondary to breast cancer. For the majority of patients this will be an extra procedure, although in a small number of cases it will be performed at disease progression or following continued patient response (i.e. if disease is not progressing). Potential risks and side effects of the procedure include infection (rare), nerve root irritation (in a minority of patients), headaches, nausea/vomiting and back pain.

IRAS ID: 286155 Page **50** of **73**

To minimise risk lumbar punctures will be performed using appropriate local anaesthesia by clinicians experienced in the procedure. Furthermore, atraumatic needles will be used which are associated with significantly less side effects than conventional needles for lumbar punctures. Where patients are undergoing a neurosurgical procedure, the lumbar puncture will be carried out once patient has been anaesthetised so reducing any side effects. Patients will be followed up to understand the side effects if any that occur post procedure²².

The information to be used for expectedness assessment for PRIMROSE CSF Study is below:

Event	Lumbar Puncture or	<pre><incidence frequency="" of<="" pre="" prevalence=""></incidence></pre>
	Ommaya Reservoir	event>*
	aspiration	
Back Pain at the time of	Lumbar Puncture	Common
injection (Bleeding, swelling		
and bruising may occur)		
Post-procedure headache	Lumbar Puncture	Common, possibly begins immediately or a
(can be associated with		few days after procedure and usually lasts
nausea and vomiting)		less than 1 week
Persisting back pain	Lumbar Puncture	Very rare
Nerve root irritation (tingling	Lumbar Puncture	Rare
or pain down the back of		
your legs)		
Brainstem herniation	Lumbar Puncture	Very very rare
Post-procedure infections ^a	Ommaya Reservoir	Very very rare
	aspiration	

^{*}These side-effects are listed on the following sites:

https://www.mayoclinic.org/tests-procedures/lumbar-puncture/about/pac-20394631

https://www.nhs.uk/conditions/lumbar-puncture/

^aPlease see section 7; 7.2 Exclusion Criteria. Where the investigator deems it unsafe to perform CSF extraction due to high risk of infection, the procedure will not be conducted.

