12.7 Notes on Safety Event Recording

It is anticipated that as lumbar puncture (with atraumatic needles) or aspiration from Ommaya Reservoir procedures carry a moderate to low risk, they will only be recommended in patients with CNS involvement secondary to breast cancer where risks-benefit ratio is favourable. For those patients, who are undergoing the procedure any safety event will be recorded if the procedure was conducted for the purposes of the study. The relevant Safety Event form will be provided for completion and the event should also be recorded in the patient notes.

[figure not shown]
IMPORTANT: Any safety events occurring after the end of the "active monitoring" period defined in Section 12.6 which meet the definition of serious should be recorded as per the guidance here if it is related to the PRIMROSE CSF Study.

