12.8.1 Reporting Safety Events to the LCTC

All safety events (whether or not assessed as serious / related / expected) should be recorded on an Adverse Event Form; multiple events can be recorded on one form.

Safety events which are assessed as "serious" must **also** be recorded in more detail on Serious Safety Event Forms; a single form is used for each individual event (i.e. a single diagnosis), though multiple symptoms can be recorded. Each SAE should have a corresponding record on the participant's AE form. Where additional information is received by site after initial submission to LCTC, this should be provided on a follow-up form within 5 days. Serious Safety Event Forms collect data regarding the nature of event, date of onset, severity, corrective therapies given, outcome and causality; all serious events reported to LCTC will be reviewed by the Chief Investigator or Clinical Coordinator and assessed for causality and expectedness.

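### Clinician-reported complications are divided by all recruited patients, although the outcome excludes neurosurgical punctures and some recruits may never have a procedure

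*Protocol*

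**What the plan says.** The complications objective in protocol section 5.4.2 carries an explicit limit: "This will not apply to patients undergoing lumbar puncture at the time of neurosurgical procedure". The objective column of the corresponding row in section 8.2 repeats it.

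The outcome column of that row has two blocks. The first is the patient questionnaire, with incidence, severity and mean duration of symptoms such as headache, backache and leg pain. No denominator is stated for these. The second is the clinician questionnaire, covering ease of the procedure, complications, and need for intravenous fluid or analgesia. It ends with "Outcomes will be percentage / proportion of patients" "over total recruited patients".

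Three other sections decide who is among the recruited:

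- The footnote to section 9.2 allows patients having a brain metastasis resected to have the puncture under general anaesthesia at the start of surgery. Section 9.5 also provides for collection at neurosurgery.
- Section 9.5 puts registration first: "Once the patient has been registered on the PRIMROSE CSF study, the patient will be scheduled in for a lumbar puncture".
- Section 10.7 allows withdrawal for withdrawn consent, investigator decision, death, or a change in condition that rules out the collection procedure.

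Section 13.5 promises counts, percentages and 95% confidence intervals. It does not restrict the denominator.

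**The concern.** One table row removes a group of patients from the outcome and then divides by a total that contains them. Recruits who are registered but withdraw or die before any CSF is taken are in that total too. Neither group can contribute a complication to this outcome, so each such patient lowers the percentage. The protocol has not left the denominator open for the analysis plan: it states one, and it conflicts with the scope of the outcome.

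Section 5.3.1 says that for most patients the procedure is additional to routine care, and section 5.3.2 says direct benefit is unlikely. The complication rate is therefore a figure that ethics committees and patients in later studies would use when a research lumbar puncture is proposed. It should describe the people who were actually exposed and assessed.

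**Working it through.** **Inputs from the protocol**

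- Denominator for the clinician block: all recruited patients (8.2).
- Group outside the outcome: punctures at neurosurgery (5.4.2, 8.2). Number not given.
- Recruits who may have no procedure: possible under 9.5 and 10.7. Number not given.
- Planned recruitment: 67 to 87 (section 7), with a target of 70 (13.2).
- Stated precision: a conservative standard error of 6% for a binary endpoint (13.2).

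**Assumed inputs, not in the protocol**

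- f, the share of recruits who are excluded or have no procedure: 10% to 40%.
- p, the complication rate among assessable patients: 10%, 20% or 30%.

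**Step 1. Reproduce the stated figure.** SE = sqrt(0.5 x 0.5 / 70) = 0.0598, which rounds to the stated 6%. This figure requires all 70 patients to be assessable.

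**Step 2. Effect of the denominator.** With N recruited, N(1 - f) patients are assessable and p x N(1 - f) of them are expected to have a complication. Dividing by N gives

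reported rate = p x N(1 - f) / N = p x (1 - f).

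The relative understatement equals f, and it vanishes only when f = 0.

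**Step 3. Numbers for N = 70**

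| f | Assessable | p = 10% reported as | p = 20% reported as | p = 30% reported as | Conservative SE on assessable patients |
|---|---|---|---|---|---|
| 10% | 63 | 9% | 18% | 27% | 6.3% |
| 20% | 56 | 8% | 16% | 24% | 6.7% |
| 30% | 49 | 7% | 14% | 21% | 7.1% |
| 40% | 42 | 6% | 12% | 18% | 7.7% |

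For example, at f = 20% and p = 20%: 0.20 x 56 = 11.2 expected events, and 11.2 / 70 = 16%. With the assessable denominator, 11.2 / 56 = 20%. The ratios at N = 67 and N = 87 are the same apart from rounding to whole patients.

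**Step 4. Second collections.** Section 3.1 aims for 20 paired collections if possible. Take 67 assessable patients, 20 of them with two procedures, a 20% risk per procedure and independence between procedures. The share of patients with at least one complication is then (47 x 0.20 + 20 x (1 - 0.80 x 0.80)) / 67 = (9.4 + 7.2) / 67 = 24.8%. This is above the 20% risk per procedure. The choice of unit therefore changes the result, and it works in the opposite direction from the denominator error.

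**The case against.** The strongest reply is that the exclusion stands in the same row, so total recruited can be taken to mean those recruits to whom the row applies. That is a charitable reading of a loose phrase. It deals with the neurosurgical patients but not with recruits who never have a procedure, and the words as written do not say it. A related reply is that the schedule in 9.5.1 lists both questionnaires at each CSF visit without exempting neurosurgical cases, so these patients might count in both numerator and denominator. That would contradict the stated exclusion.

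It is also fair to say that this is one descriptive secondary outcome, that adverse events are collected separately under section 12, and that section 13.5 promises counts beside percentages. Section 8.1 already tracks CRF return and missing key items. These facts limit the damage but do not correct the percentage.

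A reader might infer more than the protocol supports:

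- **Loss before day 28 dilutes the same rate.** The denominator phrase closes the clinician block, and sections 9.5.1 and 10.3 tie that form to the procedure visit or discharge. Day-28 loss matters only if the phrase is read over the whole row.
- **Routine-care procedures go unobserved.** Section 12.7 says "any safety event will be recorded if the procedure was conducted for the purposes of the study", while 12.8.1 says "All safety events (whether or not assessed as serious / related / expected) should be recorded on an Adverse Event Form". Both govern adverse-event forms. The questionnaires are scheduled for every CSF visit, with no exemption for routine care.
- **Late headache is missed.** Section 12.5.1 notes that it may begin a "few days after procedure and usually lasts" a limited time, but the patient questionnaire at 28 ± 7 days and adverse-event reporting up to that contact (12.6) would pick it up. Only a late need for fluid or analgesia might escape the clinician form.
- **Second procedures are left out.** Sections 9.5.1 and 10.6 repeat both questionnaires. What is unstated is how they are counted.
- **Everything biases the rate downwards.** Pooling lumbar puncture with Ommaya aspiration has no fixed direction, and separate reporting by route is a matter of presentation. Counting two procedures per patient raises the rate, as step 4 shows.

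**Conclusion.** The point holds for the denominator of the clinician-reported complications. As written, it conflicts with the exclusion in its own row and includes recruits who may have had no procedure. Taken literally, it understates the rate by a relative amount equal to f. The direction of this one error is certain whenever f exceeds zero and there are complications to count. Its size is not, because the protocol gives neither f nor an expected rate. Under the assumed 10% to 40%, a true 20% would be reported as 18% to 12%.

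The patient-questionnaire incidence has no stated denominator, so the same error cannot be asserted there. It would follow only if the phrase were carried over to that block. The conclusion does not extend to adverse-event recording, pooling of routes, or a general claim of downward bias.

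**What to change.** In section 8.2, replace the total recruited with patients who had a CSF procedure outside neurosurgery and have the relevant questionnaire completed. Then:

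- Apply the same rule to the patient-questionnaire incidence, using completion of that questionnaire.
- Report how many eligible procedures have no questionnaire, so that the reader can judge what the missing forms might hide.
- State whether the unit is the patient or the procedure when a second collection occurs.

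This is a wording change that needs no new visit or data item. The reported rate becomes somewhat less favourable. The confidence interval becomes somewhat wider: with 70 recruited, the conservative standard error would be 6.3% to 7.7% over the assumed range, against the stated 6%. That is the precision the assessable patients actually provide.
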